The CAPTURE Study: Validating a unique COPD case finding tool in primary care

Protocol Number: 1R01HL136682

National Clinical Trial (NCT) Identified Number:

NCT03581227, NCT03653611, NCT03583099

Principal Investigators:

[name]., Weill Cornell Medicine

[name]., University of Michigan

Funder:

National Heart, Lung, and Blood Institute (NHLBI)

Version Number: v. 8.0

17 July 2023

| Protocol Amendment 8.0 - Summary of Changes | | | | |
|---|-------------|----------------|--|--|
| Location | Page Number | Type of Change | Description | Rationale |
| Cover page | --- | Administrative | Update Protocol Version to 8.0 and update version date to 17JUL2023 | Amendment version and date |
| 1.1 Synopsis | 7 | Clarification | 
Secondary Endpoints
 
 • Aim 3 – O All of the above endpoints for Aim 3, in the population of participants defined by each of the following instead of CAPTURE+ status: 1) clinically significant COPD, 2) spirometric COPD, 3) Mild COPD 4) preserved ratio, impaired spirometry (PRISM), and 5) symptomatic non-obstructed (SNO) | Clarification of the secondary endpoints and what participants will be analyzed. |
| 1.3 Schedule of Assessments | 11,12 | Edit | 
Footnote 3:
 
3. Recorded for a subset of participants who meet any of the following criteria: 1) CAPTURE+ subjects defined as CAPTURE Score > 5 or CAPTURE score of 2, 3, or 4 with a low PEF, defined as <350 L/min for males and <250 L/min for females 2) abnormal spirometry defined as post-bronchodilator FEV1/FVC < 0.70 or FEV1 < 80% predicted at baseline, or pre-bronchodilator FEV1/FVC < 0.65 or FEV1 < 70% predicted for patients who do not complete post-bronchodilator spirometry; and, 3) a random sample of approximately 5% of those who do not meet criteria 1 and 2. For participants meeting criteria 1 and 2 who cannot or choose not to complete the 12-month assessment, medical record review will still be completed. For participants meeting criteria 1 and 2 who change medical practices and medical record review cannot be completed, patients will be contacted for completion of patient reported data. For participants meeting criterion 3 where all of the protocol specified 12-month assessments cannot be made, another participant will be selected at random to replace this participant.
 | The footnotes were edited to delete comment on replacing control patients who did not have availability of follow up data. |
| 1.3 Schedule of Assessments | 11 | Addition | CAPTURE questions added to 12-month evaluations | CAPTURE item additional questionnaire is to be collected at the 12-Month visit. |

| | | | | |
|--|----|---------------|---|---|
| 3.0 Objectives and Endpoints | 21 | Clarification | Aim 3 Endpoints: All of the above endpoints for Aim 3, in the population of participants defined by each of the following instead of CAPTURE+ status: 1) clinically significant COPD, 2) spirometric COPD, 3) Mild COPD , 4) preserved ratio, impaired spirometry (PRISm), and 5 4) symptomatic non-obstructed (SNO). | Clarification of the secondary endpoints and what participants will be analyzed. |
| 5.1 Inclusion Criteria | 27 | Addition | 4. Able to read and speak English or Spanish. | Study participants could complete the baseline visit and any required follow up in English or Spanish |
| 8.2 Longitudinal Follow-Up Assessments and Data Collection | 34 | Deletion | Data collected from medical record: Deleted “oral anti-inflammatory” medications Deleted * and footnote for * | This edit confirms that oral anti-inflammatory medications will not be collected during the 12-month chart review. |
| 8.2 Longitudinal Follow-Up Assessments and Data Collection | 35 | Edit | Data Collection by the COPD Foundation Deleted “oral anti-inflammatory” medications Added- CAPTURE questions Added- CAPTURE Additional Items Questionnaire Deleted * and footnote for * | Data collected by the COPD Foundation will now include CAPTURE Questions and CAPTURE Additional Item Questionnaire. |
| 9.3.2 Practice Behavior (Aim 3) | 47 | Addition | All additional secondary analyses will also be applied to patients with clinically significant and spirometrically defined COPD, Mild COPD , PRISm, and symptomatic non-obstruction. | Secondary analyses include Mild COPD as reflected throughout the protocol. |

| ANCOVA | Analysis of Covariance |
| CAO | Chronic Airflow Obstruction |
| CFR | Code of Federal Regulations |
| CLIA | Clinical Laboratory Improvement Amendments |
| CMP | Clinical Monitoring Plan |
| COC | Certificate of Confidentiality |
| CONSORT | Consolidated Standards of Reporting Trials |
| COPD | Chronic Obstructive Pulmonary Disease |
| CRF | Case Report Form |
| DCC | Data Coordinating Center |
| DHHS | Department of Health and Human Services |
| DSMB | Data and Safety Monitoring Board |
| DRE | Disease-Related Event |
| EC | Ethics Committee |
| eCRF | Electronic Case Report Forms |
| ECOPD | Exacerbation of Chronic Obstructive Pulmonary Disease |
| FDA | Food and Drug Administration |
| FDAAA | Food and Drug Administration Amendments Act of 2007 |
| FEV1 | Forced Expiratory Volume in 1 second |
| FFR | Federal Financial Report |
| FVC | Forced Vital Capacity |
| GCP | Good Clinical Practice |
| GLP | Good Laboratory Practices |
| GMP | Good Manufacturing Practice |
| GWAS | Genome-Wide Association Studies |
| HIPAA | Health Insurance Portability and Accountability Act |

| | |
|---------|---|
| IB | Investigator's Brochure |
| ICH | International Conference on Harmonisation |
| ICMJE | International Committee of Medical Journal Editors |
| IDE | Investigational Device Exemption |
| IND | Investigational New Drug Application |
| IRB | Institutional Review Board |
| ISM | Independent Safety Monitor |
| ISO | International Organization for Standardization |
| ITT | Intention-To-Treat |
| LSMEANS | Least-squares Means |
| MedDRA | Medical Dictionary for Regulatory Activities |
| MOP | Manual of Procedures |
| MSDS | Material Safety Data Sheet |
| NCT | National Clinical Trial |
| NIH | National Institutes of Health |
| NIH IC | NIH Institute or Center |
| OHRP | Office for Human Research Protections |
| PBRN | Practice-Based Research Network |
| PI | Principal Investigator |
| PRISm | Preserved ratio, impaired spirometry |
| QA | Quality Assurance |
| QC | Quality Control |
| RE-AIM | Reach, Effectiveness, Adoption, Implementation, Maintenance |
| SAE | Serious Adverse Event |
| SAP | Statistical Analysis Plan |
| SMC | Safety Monitoring Committee |
| SNO | Symptomatic non-obstructed |
| SOA | Schedule of Activities |
| SOC | System Organ Class |
| SOP | Standard Operating Procedure |
| UP | Unanticipated Problem |
| US | United States |
| USPSTF | United States Preventive Services Task Force |

1 PROTOCOL SUMMARY

1.1 SYNOPSIS

| | |
|---------------------------|--|
| Title: | The CAPTURE Study: Validating a unique Chronic Obstructive Pulmonary Disease (COPD) case finding tool in primary care |
| Study Description: | 
Aims 1 and 3. A prospective, multicenter study including a cross-sectional validation to define sensitivity and specificity of CAPTURE and its impact on clinical care across a broad range of primary care settings in a cluster randomized controlled clinical trial. The CAPTURE tool consists of a 5-item self-administered questionnaire and peak expiratory flow (PEF) measurement, designed to identify undiagnosed patients with Chronic Obstructive Pulmonary Disease (COPD).
 
Aim 2. This study delivers a qualitative assessment of clinical practice acceptance of and implementation strategy for CAPTURE case finding within 10 varied primary care practices across 5 US PBRN regions. We evaluate primary care practice attitudes, beliefs and recommendations about CAPTURE's potential to feasibly integrate into clinical practice patterns, workflow and quality improvement paradigm planning in a variety of primary care clinical settings.
 |
| Definitions: | 
CAPTURE+ = Participants with
 
• CAPTURE score ≥ 5, or• CAPTURE score of 2, 3, or 4 with a low PEF, defined as <350 L/min for males and <250 L/min for females 
CAPTURE- = Participants with CAPTURE score < 2 or scores 2-4 with normal PEF, defined as ≥ 350 L/min for males and ≥ 250 L/min for females
 
Spirometrically defined COPD = Participants with abnormal spirometry, defined as post-bronchodilator $FEV_1/FVC < 0.7$. If a participant is unable to complete a post-bronchodilator spirometry (refusal, technical error on the part of coordinator, etc.), and the pre-bronchodilator FEV_1/FVC is less than 0.65, the participant will be considered to have COPD for the purpose of follow-up in this study.
 
Clinically significant COPD = Participants with abnormal spirometry, defined as post-bronchodilator $FEV_1/FVC < 0.7$, plus one of the following:
 
• $FEV_1 < 60\%$ predicted, or• ≥ 1 exacerbation-like event within the past 12 months. 
Mild COPD = Participants with abnormal spirometry, defined as post-bronchodilator $FEV_1/FVC < 0.7$ plus both of the following:
 
• $FEV_1 \geq 60\%$ and• No prior history of ECOPD 
Preserved ratio, impaired spirometry (PRISm) = Participants without spirometrically defined COPD who have post-bronchodilator $FEV_1 < 80\%$ predicted.
 
Symptomatic non-obstructed (SNO) = Participants without spirometrically defined COPD and without PRISm who have a COPD Assessment Test score ≥ 10.
 |

| | |
|--------------------|--|
| Objectives: | Aims 1 and 3 Primary Objectives: 
• Aim 1 - Define the sensitivity and specificity of CAPTURE for identifying previously undiagnosed patients with clinically significant COPD in a broad range of primary care settings. |
| | 
• Aim 3 – Define the impact of CAPTURE information provided to clinicians in identifying and managing CAPTURE+ patients across a broad range of primary care settings. 
Aim 2 Primary Objective: Explore clinical practice implementation approaches to and acceptance of CAPTURE case finding for clinically significant COPD in a range of primary care practices.
 |

| | |
|--|--|
| | 
Aims 1 and 3 Secondary Objectives:
 
• Aim 1 –• Define the sensitivity and specificity of CAPTURE for patients with COPD across a broad range of racial and ethnic groups in a range of primary care settings.• Determine positive and negative predictive values (PPV and NPV) in different practice settings.• Verify the optimal use (cutoff threshold) of the CAPTURE tool in combination with PEF measurements for identifying undiagnosed COPD.• Determine patient and site characteristics that, with the CAPTURE assessment, will best identify persons with undiagnosed COPD.• Determine whether CAPTURE is useful in identifying other definitions of undiagnosed COPD including:
1) spirometry-defined COPD, and2) mild COPD• Determine the potential impact of SARS CoV-2 infection on the above operating characteristics of the CAPTURE approach. 
• Aim 3 -
 
• Define the impact of providing CAPTURE education and patient-level CAPTURE information to clinicians on selected clinician interventions for the management of CAPTURE+ patients.• Assess the impact of CAPTURE education and patient-level CAPTURE information on clinician interventions specific to smokers who are CAPTURE+.• Determine the impact of CAPTURE education and patient-level CAPTURE information on patient symptoms, exacerbations, hospitalizations, and mortality among CAPTURE+ patients.• Determine the impact of CAPTURE education and receipt of patient-level CAPTURE information on identification and management of patients with respiratory burden.• Determine the potential impact of SARS CoV-2 infection on clinical actions taken in response to CAPTURE screening. 
Aim 2 Secondary Objectives:
 
• Qualitatively assess primary care clinical staff COPD practice behavior – including COPD screening and diagnostic perceptions, beliefs and knowledge – that will inform strategies to improve CAPTURE RE-AIM (reach, impact, adoption, implementation and maintenance of use) characteristics. |
|--|--|

[figure not shown]
| | |
|-------------------|--|
| | 
Qualitatively assess primary care patient opinion of CAPTURE COPD case finding that will inform strategies to improve CAPTURE RE-AIM (reach, impact, adoption, implementation and maintenance of use) characteristics.Determine the potential impact of SARS CoV-2 infection on the application of the CAPTURE approach. |
| Endpoints: | 
Aims 1 and 3 Primary Endpoints:
 
Aim 1 –
Sensitivity and specificity of CAPTURE to identify previously undiagnosed patients with clinically significant COPD at baseline.Aim 3 –
Proportion of CAPTURE+ participants who meet at least one of the following within 12 months of study baseline (composite endpoint): 1) referral for or completion of clinical spirometry testing, 2) new diagnosis of COPD, 3) newly prescribed respiratory medication (long acting bronchodilator or anti-inflammatory for respiratory condition), 4) referral to a specialist for respiratory evaluation/treatment, or 5) referral for or completion of pulmonary rehabilitation. 
Aim 2 Primary Endpoints:
 
Primary care clinician recommendations that inform CAPTURE RE-AIM strategies at both provider and clinical support levels of primary care practice.Primary clinician recommendations that inform CAPTURE-associated COPD education models for primary care clinicians.Primary care clinician recommendations that inform CAPTURE-associated COPD clinical quality improvement designs across a variety of primary care practice types. 
Aims 1 and 3 Secondary Endpoints:
 
Aim 1 –
Sensitivity and specificity of CAPTURE to identify previously undiagnosed patients with COPD across sex, ethnic groups, urban vs rural location, and educational level.Positive and negative predictive values (PPV and NPV) in different practice settings.Areas under the receiving operator characteristic curve (AUC) for various cutpoints of CAPTURE and PEF₁ measurements to determine the best cutpoint for COPD+ screen.AUC to identify the combination of patient/site characteristics which best discriminates those with clinically significant COPD.All primary and secondary endpoints as applied to 1) spirometry-defined COPD and 2) mild COPDAim 3 –
Proportion of CAPTURE+ participants who have each of the following occur within 12 months of study baseline (separate endpoints to be evaluated individually): 1-5) each component of the Aim 3 primary endpoint, and 6) recommendation or administration of influenza vaccination. |

| | |
|--------------------------|---|
| | 
○ Proportion of CAPTURE+ participants currently smoking at the baseline study visit who have any of the components of the Aim 3 primary endpoint or any of the following occur within 12 months of baseline (evaluated as a composite endpoint and as individual endpoints): 1) clinician counseling or recommendation for smoking cessation, 2) referral to a smoking cessation program, 3) referral to a smoking quit line, and 4) newly prescribed medication for smoking cessation.○ In CAPTURE+ participants, change in CAT score between baseline and follow-up at 12 months after baseline, and proportion of patients who experience exacerbations, hospitalizations, or mortality within 12 months of baseline.○ All of the above endpoints for Aim 3, in the population of participants defined by each of the following instead of CAPTURE+ status: 1) clinically significant COPD, 2) spirometric COPD, 3) Mild COPD, 4) preserved ratio, impaired spirometry (PRISM), and 5) symptomatic non-obstructed (SNO).○ All of the above endpoints for Aim 3, in all of the analysis populations named above, separated into cohorts based on enrollment date and the degree to which follow-up may have been affected by the SARS-CoV-2 pandemic. 
Aim 2 Secondary Endpoints:
 
● Existing COPD screening and diagnostic and case finding processes within a variety of primary care practices.● Primary care practice belief about capacity to change from existing COPD screening and diagnostic assessment strategies.● Practice-specific COPD screening and diagnostic continuing education preference. |
| Study Population: | 
Aims 1 and 3. Adults 45-80 years old without a prior diagnosis of COPD (total N ~ 5000)
 
Aim 2.
 
- 10 primary care practices: 2 practices per PBRN with up to 15 clinical staff participants per practice; clinician N = up to 150 (up to 30 clinician participants per PBRN).- Aim 1 patient opinion survey population; patient N = 200 (40 patients from each PBRN; adults 45-80 years old, without a prior diagnosis of COPD).- Total N = up to 350 |
| Phase: | N/A |

| | |
|--|--|
| Description of Sites/Facilities Enrolling Participants: | 
Aims 1 and 3. Enrollment will occur in approximately 100 primary care practices affiliated with 7 primary care based practice networks (PBRN) across the United States who exhibit a broad range of gender, ethnic, racial, socioeconomic, and regional diversity.
 
Aim 2.
 
• Two primary care practices chosen by each of the same 5 PBRN co-investigator teams make up the 10 aim 2 practices from which clinician participants are enrolled. These 10 practices are separate from the 100 chosen practices in aims 1 and 3.• Patient participants are a sub-sample of those participants enrolled in aims 1 and 3. |
| Description of Study Intervention: | 
Aims 1 and 3. Primary care practices will be randomized to either receive basic COPD education and patient-level CAPTURE information with CAPTURE education (initially basic then later enhanced based on data collected in Aim 2) versus COPD education only.
 
Aim 2. Participating primary care clinicians from 10 varied practices are surveyed at three different time points and participate in two focus groups qualitatively assessing CAPTURE implementation strategy and COPD case finding approaches in primary care. Participating patients complete one 10-minute written opinion survey about CAPTURE.
 |
| Study Duration: | 
Aim 1 and 3. 4 years
 
Aim 2. 2 years
 |
| Participant Duration: | 
Aims 1 and 3. Up to 12 months
 
Aim 2.
 
• Primary care practice clinicians: questionnaires and focus groups (total 3 hours/participant) over 16 months.• Primary care patients: one 10-minute questionnaire/participant over 14 months. |

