| OBJECTIVES | ENDPOINTS | JUSTIFICATION FOR ENDPOINTS |
|--|---|---|
| Aim 1: Determine patient and site characteristics that, with the CAPTURE assessment, will best identify persons with undiagnosed COPD. | AUC to identify the combination of patient/site characteristics which best discriminates those with clinically significant COPD. | The best discrimination will determine which site and patient characteristics best predicted undiagnosed COPD in combination with the CAPTURE tool. |
| Aim 1: Determine whether CAPTURE is useful in identifying other definitions of undiagnosed COPD: 1) spirometry-defined COPD, and 2) mild COPD | All primary and secondary endpoints as applied to 1) spirometry-defined COPD and 2) mild COPD | This will determine the robustness of the CAPTURE tool. |
| Aim 3: Define the impact of providing CAPTURE education and patient-level CAPTURE information to clinicians on selected clinician interventions for the management of CAPTURE+ patients. | Proportion of CAPTURE+ participants who have each of the following occur within 12 months of study baseline (separate endpoints to be evaluated individually): 1-5) each component of the Aim 3 primary endpoint, and 6) recommendation or administration of influenza vaccination. | Each endpoint is clinically relevant and consistent with published data. (45) This will test the impact of CAPTURE on clinician behavior. |
| Aim 3: Assess the impact of CAPTURE education and patient-level CAPTURE information on clinician interventions specific to smokers who are CAPTURE+. | Proportion of CAPTURE+ participants currently smoking at the baseline study visit who have any of the components of the Aim 3 primary endpoint or any of the following occur within 12 months of baseline (evaluated as a composite endpoint and as individual endpoints): 1) clinician counseling or recommendation for smoking cessation, 2) referral to a smoking cessation program, 3) referral to a smoking quit line, and 4) newly prescribed medication for smoking cessation. | Certain outcomes are specific to only smokers and should be assessed. |
| OBJECTIVES | ENDPOINTS | JUSTIFICATION FOR ENDPOINTS |

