9.3.2 PRACTICE BEHAVIOR (AIM 3)

The primary analysis of the Aim 3 primary endpoint will be to compare the average cluster sample proportion (average proportion of CAPTURE+ patients per practice meeting composite endpoint) between intervention arms. Practices that do not identify any CAPTURE+ subjects will not contribute to the primary analysis. The primary analysis is a two-sample test comparing average cluster sample proportions that explicitly takes into account correlation between individuals treated within the same practice. A two-sided p-value < 0.05 will be considered statistically significant. This analysis corresponds to a generalized estimating equation (GEE) regression analysis with (1) individual-level binary composite outcome data, (2) CAPTURE intervention group as a covariate, (3) practice id used to identify correlated outcomes, (4) exchangeable correlation matrix that assumes similar correlation between all composite outcome results for patients within the same practice, and (5) an identity link function so that the coefficient parameter corresponding to CAPTURE intervention group represents a difference in outcome probability. The primary analysis would then correspond to a test for whether the CAPTURE intervention group parameter is non-zero. There are no planned interim analyses for the primary endpoint, the rationale being that this is not a pharmaceutical or device trial that would benefit from standard stopping rules for efficacy. A DSMB will be monitoring the study for safety and study integrity.

Secondary analyses on meeting the composite outcome for participants who are CAPTURE+ will employ the GEE analysis framework with individual and practice level predictors in addition to the CAPTURE intervention group. Interactions will be assessed. We will also use the GEE framework to study and describe each of the individual components of the composite outcome as they relate to individual and practice level outcomes. In the subset of smoking patients, we will use GEE regression analysis to study additional binary outcomes, such as incidence of physician counselling/recommendation to stop smoking, physician referral to a formal smoking cessation program, newly prescribed smoking cessation medication, and referral to a smoking quit line.

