| Assess the impact of CAPTURE education and patient-level CAPTURE information on clinician interventions specific to smokers who are CAPTURE+. | Proportion of CAPTURE+ participants currently smoking at the baseline study visit who have any of the components of the Aim 3 primary endpoint or any of the following occur within 12 months of baseline (evaluated as a composite endpoint and as individual endpoints): 1) clinician counseling or recommendation for smoking cessation, 2) referral to a smoking cessation program, 3) referral to a smoking quit line, and 4) newly prescribed medication for smoking cessation. |
| Determine the impact of CAPTURE education and patient-level CAPTURE information on patient symptoms, exacerbations, hospitalizations, and mortality among CAPTURE+ patients. | In CAPTURE+ participants, change in CAT score between baseline and follow-up at 12 months after baseline, and proportion of patients who experience exacerbations, hospitalizations, or mortality within 12 months of baseline. |
| Determine the impact of CAPTURE education and patient-level CAPTURE information on identification and management of patients with respiratory burden. | All of the above endpoints for Aim 3, in the population of participants defined by each of the following instead of CAPTURE+ status: 1) clinically significant COPD, 2) spirometric COPD, 3) preserved ratio, impaired spirometry (PRISM), and 4) symptomatic non-obstructed (SNO). |
| Determine the potential impact of SARS CoV-2 infection on clinical actions taken in response to CAPTURE screening. | All of the above endpoints for Aim 3, in all of the analysis populations named above, separated into cohorts based on enrollment date and the degree to which follow-up may have been affected by the SARS-CoV-2 pandemic. |

6 Study Methods for Cluster Randomized Trial (CAPTURE Protocol Aim 3)

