9.7 Multiple Testing

Two-sided p-values will be reported. When the primary analysis is repeated for each component of the primary endpoint (spirometry referral/completion, new COPD diagnosis, newly prescribed inhaled medication, referral to a respiratory specialist, and pulmonary rehabilitation referral/completion), a Bonferroni correction will be applied to that set of hypothesis tests. Otherwise, no adjustments for multiplicity will be made across analyses of primary and secondary endpoints and other exploratory analyses. Thus, corresponding p-values for these secondary and exploratory outcomes will be interpreted with caution. Confidence intervals will be provided to summarize treatment differences for efficacy end points.

10 Summary of Study Conduct Data

Descriptive summary statistics will be tabulated for baseline patient demographics and clinical characteristics as well as practice characteristics, separately by intervention group and overall. Intervention groups will be characterized as “Basic COPD Education” and “Basic COPD plus CAPTURE Education”. For pooled summaries, “All” will be used as the column heading. All tables will be annotated with the total population size relevant to that table, including any missing observations.

For continuous variables, sample means and standard deviations will be reported. P-values corresponding to two-sample t-tests¹ comparing mean differences between intervention groups will be reported. For categorical variables, number and percentages will be reported (excluding missing values). P-values corresponding to Pearson’s² chi squared statistic or Fisher’s³ Exact test for testing association between categorical predictors and intervention groups, as appropriate, will be given.

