11.2 Secondary Efficacy Analyses

Secondary Analyses of Primary Outcome: The primary analysis as described in section 11.1 will be repeated in analysis populations 2-8 as given in section 9.3 overall and by subgroups described in section 9.4. For analysis population 1, the primary analysis as described in section 11.1 will be repeated in subgroups described in section 9.4.

In addition, multivariable GEE regression analyses will be conducted separately in populations 1-8 from section 9.3, where the primary composite outcome is modelled using individual and practice level predictors in addition to the CAPTURE intervention group. Interactions will be assessed.

Efficacy Analyses of Secondary Outcomes: All analyses in this section will be conducted (separately) for each study population 1 through 8 described in section 9.3 overall and by subgroups described in section 9.4.

We will use the GEE framework to study and describe each of the individual components of the composite outcome as they relate to the CAPTURE intervention group.

In the subset of patients who report being current smokers at baseline, we will study additional binary outcomes, such as incidence of physician counselling/recommendation to stop smoking, physician referral to a formal smoking cessation program, newly prescribed smoking cessation medication, and referral to a smoking quit line, individually and in a composite outcome that also incorporates the primary outcome components.

Multivariable GEE models will incorporate individual and practice level covariates into the analysis of individual components of the composite outcome. Model selection in multivariable secondary analyses will be based on statistical significance at the 0.05 level using GEE robust sandwich estimation of variability within clusters. Model fit will be checked by comparing observed versus predicted values within predefined subgroups of interest as given in section 9.4.

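### The only composite for the smoker-specific objective also counts all five primary-endpoint components, and no overall cessation-only measure is planned or named as the answer to that objective

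*Protocol*

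**What the plan says.** The objective (Protocol 1.1 and 3; SAP Table 1) concerns "clinician interventions specific to smokers who are CAPTURE"+. Protocol section 3 justifies the endpoint thus: "Certain outcomes are specific to only smokers and should be assessed".

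The endpoint is a proportion within the CAPTURE+ group, namely those "currently smoking at the baseline study visit who have any of the components of the Aim 3 primary endpoint or any of the following": cessation counselling or recommendation, cessation-programme referral, quit-line referral, or new cessation medication. It is "evaluated as a composite endpoint and as individual endpoints".

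On analysis:

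- Protocol 9.3.2 covers the single items: "In the subset of smoking patients, we will use GEE regression analysis to study additional binary outcomes". It does not mention the mixed composite.
- SAP 11.2 takes the four items "individually and in a composite outcome that also incorporates the primary outcome components".
- SAP 9.4 lists smoking status (current, former, never) as a subgroup. SAP 11.2 repeats the primary composite and its components by those subgroups.
- SAP 9.5, when organising the imputation, puts the five primary components in a pulmonary-care group and the four cessation actions in a separate smoker-specific group.
- SAP 9.7 applies Bonferroni to the five primary components only: "Otherwise, no adjustments for multiplicity will be made across analyses of primary and secondary endpoints and other exploratory analyses".

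**The concern.** The objective and its justification point to smoking-specific care, but the composite attached to them is mostly made of other things. Spirometry, COPD diagnosis, respiratory medication, specialist referral and pulmonary rehabilitation are not specific to smokers, and all five are already tested as the primary endpoint and its components. A shift in spirometry referral alone moves the smoker composite.

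If the intervention works on the primary endpoint, the smoker composite may also be positive with no change in cessation care. Beside it would stand four single-item results with no multiplicity rule and no summary measure over them. Neither document says which of these five results answers the question about smokers. A report would have to choose after seeing the data.

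**Working it through.** **The plan's own power figures.** There is none for the smoker endpoint. Table 9-2, which supplies the primary-effect sizes used here, reproduces. With n per arm = 44 × 5 / (1 + 4 × ICC), two-sided 5% and a 5% control rate, ICC 0.10 gives n = 220 / 1.4 = 157 and power 0.654, 0.843 and 0.983 for +7.5, +10 and +15 points. The table states 0.65, 0.84 and 0.98.

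**How much of the primary effect passes through.** Let p0 and p1 be the primary-endpoint rates in CAPTURE+ smokers by arm (taken as equal to the overall rates), and c the rate of at least one cessation action. Assume c is the same in both arms and independent of respiratory actions.

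- Composite rate in an arm = 1 − (1 − p)(1 − c)
- Difference between arms = (1 − c)(p1 − p0)

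| c | primary 5% to 20% | primary 5% to 30% |
|---|---|---|
| 30% | 0.70 × 15 = 10.5 points | 0.70 × 25 = 17.5 points |
| 50% | 7.5 points | 12.5 points |
| 70% | 4.5 points | 7.5 points |
| 85% | 2.25 points | 3.75 points |

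At c = 30% and a +15-point effect, the composite is 33.5% against 44.0% although cessation care is identical.

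**How often the composite would be significant.** Assumptions:

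- 50 practices per arm (Protocol 9.1.1.3).
- 2.5 CAPTURE+ smokers per practice: an assumed 25% of the 10 CAPTURE+ per practice in SAP 13.1.
- A lower case of 2.5 × 0.65 = 1.6, because the primary analysis needs both chart and survey data and the one survey completion figure in SAP 13.1 is 248/380 = 65%.
- ICC 0.05, beta-binomial practices, Poisson cluster sizes, practice-level robust variance, no cessation effect.

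For a +15-point primary effect (range = 1.6 to 2.5 smokers per practice):

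| c | mixed composite | cessation-only composite |
|---|---|---|
| 30% | about 27–37% | about 5–6% |
| 50% | about 16–21% | about 5–6% |
| 70% | about 9–12% | about 5–6% |
| 85% | about 7–9% | about 5–6% |

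For a +25-point effect the mixed composite is significant in about 62–77% (c = 30%), 35–49% (c = 50%) and 19–25% (c = 70%).

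**Cross-check by formula.** With 44 practices per arm, 2 smokers each and ICC 0.10, the effective n per arm is 88 / 1.1 = 80. For +15 points at c = 30%, the standard error is √[(0.335 × 0.665 + 0.44 × 0.56) / 80] = 0.077. Then 0.105 / 0.077 = 1.37, and the chance of a positive result is 0.28. At c = 50% it is 0.16 and at c = 80% it is 0.07. For +25 points the three values are 0.62, 0.37 and 0.13. The pattern is the same.

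**The case against.** The strongest reply is that the plan does not rest on the composite alone. The sentence defining the endpoint also calls for individual endpoints, and both documents plan separate analyses of all four cessation actions. With the primary composite and its components repeated in current smokers, a reader will see whether a positive mixed composite comes from spirometry referral or from cessation care. This stands. It rules out the inference that an absent cessation effect would be hidden.

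A reader might also call the significant results above false positives. They are not: the mixed composite's own null hypothesis is false in those scenarios. Any respiratory or cessation action among smokers is a legitimate, broader quantity, and the SAP says openly what it contains. Nor do the documents say that a positive mixed composite will be reported as better cessation care.

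The size is uncertain as well. The cessation rate, the smoker share and independence are all assumed. If respiratory and cessation actions tend to fall on the same patients, less of the primary effect would usually pass through. Where background counselling is common, the composite is diluted more than it is driven by the primary components.

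Finally, Protocol 9.1.2.2 calls these analyses exploratory and unpowered, and SAP 9.7 asks for caution with unadjusted p-values. That limits the severity. It does not supply the missing measure: four single-item tests give no overall answer on cessation care, and no result is designated as the answer.

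**Conclusion.** The concern holds in a limited form. The only composite for the smoker-specific objective does not match that objective and passes on (1 − c) of any primary effect when cessation care is unchanged. For +15 points that means a significant result in roughly 7–9% of trials at c = 85% and up to 27–37% at c = 30%, under smoker counts, an ICC and independence that the documents do not establish. The figures are a range, not a forecast.

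The documents do not support the stronger readings: that the smoker endpoint is solely this composite, that nothing in the plan could reveal its source, or that the composite should be withdrawn. The gap is the lack of an overall cessation-only test and of a designated lead result. Severity is low to moderate, and the primary analysis is untouched.

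**What to change.** In Protocol 1.1 and 3 and SAP Table 1 and 11.2:

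1. Add a composite of at least one of the four cessation actions, which is the smoker-specific group already listed in SAP 9.5, and name it the lead measure for this objective.
2. Keep the four individual endpoints.
3. Keep the mixed composite as supportive. Report it beside the primary-composite result in current smokers, and state that it is not evidence on cessation care.

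No new data are needed: Protocol 8.2 and SAP Table 3 already collect all four actions from the medical record. The cost is a few lines of wording, one more exploratory secondary analysis, and a lower event rate than the mixed composite.
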